**Table 2: Placebo or Givinostat Starting Dose**

Weight (kg)	≥10 and < 12.5	≥12.5 and < 20	≥20 and < 25	≥25 and < 30	≥30 and < 40	≥40 and < 50	≥50 and < 60	≥60 and < 70	≥70
Dose (mg) bid	13.3	16.7	20	23.3	26.7	33.3	36.7	40	46.7
Oral suspension (mL) bid	1.3	1.7	2.0	2.3	2.7	3.3	3.7	4	4.7

The subjects who were randomized under protocol version 4.0 will continue the current dose (see Table 4).

**Table 3: Placebo or Givinostat Starting Dose for subjects enrolled under Protocol version 4.0**

Weight (kg)	≥10 and <12.5	≥12.5 and <20	≥20 and <25	≥25 and <30	≥30 and <40	≥40 and <50	≥50 and <60	≥60 and < 70	≥70
Dose (mg) bid	20	25	30	35	40	50	55	60	70
Oral suspension (mL) bid	2.0	2.5	3.0	3.5	4.0	5.0	5.5	6.0	7.0

### **Dose Modifications for subjects randomized under protocol version 6.0 or 7.0 or 8.0:**

Study drug dose adjustment including safety rules for permanently or temporarily stopping study drug are described in Section 7.3.1.

As mentioned in Section 7.3.1, in case a subject has a consistent (e.g., at least 2 consecutive evaluations) platelets count  $\leq 150 \times 10^9/L$  and but does not meet the stopping criteria due to platelet reduction, the Investigator will have to reduce the dose by 20% of the current dose (first example: e.g., starting dose = 20 mg bid  $\rightarrow$  20% dose reduction  $\rightarrow$  new dose = 16 mg bid; second example: starting dose = 26.7 mg bid  $\rightarrow$  20% dose reduction  $\rightarrow$  new dose = 21.4 mg bid) (see Table 4).

**Table 4: Placebo or Givinostat Dose Modification for subjects randomized under study protocol version 6.0 or 7.0 or 8.0.**

Weight (kg)	$\geq 10$ and $< 12.5$	$\geq 12.5$ and $< 20$	$\geq 20$ and $< 25$	$\geq 25$ and $< 30$	$\geq 30$ and $< 40$	$\geq 40$ and $< 50$	$\geq 50$ and $< 60$	$\geq 60$ and $< 70$	$\geq 70$
Starting Dose (mg) bid	13.3	16.7	20	23.3	26.7	33.3	36.7	40	46.7
Oral suspension (mL) bid	1.3	1.7	2.0	2.3	2.7	3.3	3.7	4	4.7
Reduced Dose (mg) bid	10.6	13.4	16	18.6	21.4	26.6	29.4	32	37.4
Oral suspension (mL) bid	1.1	1.3	1.6	1.9	2.1	2.7	2.9	3.2	3.7

Study drug can be resumed at a level 20% smaller than the dose at which the AE leading to temporary stop occurred, once platelets and/or white blood cell and/or hemoglobin are normalized and/or triglycerides return to levels below 300 mg/dL (3.42 mmol/L) or when diarrhoea is mild.

For subjects randomized under protocol version 6.0 or 7.0 or 8.0, only one dose reduction is allowed during the treatment period.

**Dose Modifications for subjects randomized under protocol version 4.0:**

The subjects who were randomized under protocol version 4.0, will follow the dose modification instruction as per protocol version 4.0, as described below in Table 5.

**Table 5: Placebo or Givinostat Dose Modification for subject randomized under study protocol version 4.0**

Weight (kg)	≥10 and <12.5	≥12.5 and <20	≥20 and <25	≥25 and <30	≥30 and <40	≥40 and <50	≥50 and <60	≥60 and < 70	≥70
Starting Dose (mg) bid	20	25	30	35	40	50	55	60	70
Oral suspension (mL) bid	2.0	2.5	3.0	3.5	4.0	5.0	5.5	6.0	7.0
Reduced Dose (mg) bid	13.3	16.7	20	23.3	26.7	33.3	36.7	40	46.7
Oral suspension (mL) bid	1.3	1.7	2.0	2.3	2.7	3.3	3.7	4	4.7

Study drug dose adjustment including safety rules for permanently or temporarily stopping study drug are described in Section 7.3.1.

As mentioned in Section 7.3.1, in case a subject has a consistent (e.g., at least 2 consecutive evaluations) platelets count  $\leq 150 \times 10^9/L$  and does not meet the stopping criteria due to platelet reduction, the Investigator will have to reduce the dose by 1/3 of the starting dose (see Table 5).

Study drug can be resumed at a level 1/3 smaller than the dose at which the AE leading to temporary stop occurred, once platelets and/or white blood cell and/or hemoglobin are normalized and/or triglycerides return to levels below 300 mg/dL (3.42 mmol/L) or when diarrhoea is mild.

If a subject was randomized with baseline triglycerides above 300 mg/dL (3.42 mmol/L), the Investigator can discuss how to manage the case with the medical monitor, however the final decision remain with the Investigator or its authorized designee only.

Moreover, for subjects who have already reduced the dose of 1/3 an additional reduction by 20% is allowed for safety reasons following the instruction reported in Table 4.

**Dose Modification (all subjects):**

If subjects (i.e. those already in treatment or those who will be randomized under protocol version 6.0 or 7.0 or 8.0) gain weight during the study the drug dose must be kept unchanged.

If subjects (i.e. those already in treatment or those who will be randomized under protocol version 6.0 or 7.0 or 8.0) lose weight during the study, the drug dose should be adjusted

according to Table 2 or Table 3 if the subject is still on treatment at starting dose, or according to Table 4 or Table 5 if the subject has already reduced the starting dose.

All subjects will be asked to have platelets count assessments weekly during the first month of treatment and performed every two weeks during the second month of treatment, in order to strictly monitor this parameter for safety reasons.

If the dose is reduced due to platelet count  $\leq 150 \times 10^9/L$ , and/or white blood cell  $< 3.0 \times 10^9/L$  and/or hemoglobin  $< 10.0 \text{ mg/dL}$  a complete blood count (i.e.CBC) test must be performed weekly for 8 consecutive weeks.

If a dose adjustment and/or modification of schedule of assessments is decided by the Investigator or authorized designee, it is advised to discuss this decision with the Medical Monitor, however this is not mandatory as the Investigator is the only responsible for the medical care of the subject and the Investigator's decision should not be influenced, deleted nor approved by the Medical Monitor.

### **8.3 Study Treatment Assignment**

The Investigator will be responsible for the delivery of study drug to the subject's parent/legal guardian according to the protocol. Subjects will be administered the study drug on an outpatient basis. All study drug supplies are to be used only for this protocol and for no other purpose.

At Visit 3, subjects fulfilling all inclusion criteria and none of the exclusion criteria will be randomised via interactive response technology (IRT). During the randomization procedure, the Investigator will be asked to record the type of steroid used by the subject (i.e. Deflazacort or other type of steroids) and to record the regimen of intake (i.e. daily regimen or intermittent regimen) following the instruction provided in the IRT manual. The IRT will assign the subject to one stratum according to the collected information (i.e. Deflazacort Daily regimen, Deflazacort Intermittent regimen, Other steroids Daily regimen, Other steroids Intermittent regimen) and them to a treatment arm in a 2:1 ratio to receive givinostat or placebo.

During the first 3 months, the Investigator will supply the child's parent/legal guardian with the appropriate number of suspension bottles sufficient to cover one month of treatment at scheduled visits (i.e., at Visit 3, 7 and 9). Then, for the remaining part of the study (i.e., at

Visit 10, 11, 12, 13, and 14, the Investigator will supply the child's parent/legal guardian with the appropriate number of suspension bottles sufficient to cover the period between two visits (i.e., 3 months of treatment).

The Investigator is to call using IRT at each dispensing visit in order to obtain the packaging number of the study treatment to be dispensed to the subject by the subject's parent/legal guardian.

Study treatment should be dispensed to each subject's parent/legal guardian by authorized personnel only.

The Investigator will provide to the subject parent/legal guardian written instruction on the dosage and corresponding volume in milliliters of suspension to be taken at each administration. Refer to the relevant Clinical Study Operations Manual (CSOM) for more detailed information.

#### **8.4 Blinding**

This is a double-blind, placebo controlled study, so subjects receiving givinostat or placebo will receive medication indistinguishable in appearance. Personnel involved in the study (Investigators, nurses, all other site personnel, clinical research associate (CRA), Medical Monitors, Project Managers, and personnel involved in data management) will remain blind at all times, unless under exceptional circumstances when knowledge of the study drug is essential for treating the subject, such as in case of an AE. If the Investigator or authorized designee decides to break the code of a subject, it is suggested that the Monitoring Team (Medical Monitor or CRA) would be consulted if possible before breaking the code, however this is not mandatory because the decision of the Investigator cannot be influenced, deleted nor approved by the Monitoring Team.

Code breaking can be performed by the Investigator or authorized designee at any time by using the proper module of the IRT system.

If the code is broken, treatment with the study drug must be stopped.

In any case, after breaking the code, the Investigator must record the date, time, and reason for breaking the code in the CRF, and must notify the Monitoring Team as soon as possible.

As platelets count reductions are observed after treatment with givinostat, study site personnel who will perform functional tests and MRI/MRS must be different from the personnel who will review subjects' safety results and safety results must not be shared with the personnel responsible for the functional tests and MRI/MRS.

Regarding the PK results, all the personnel involved in the study will remain blind at all times and Sponsor may review the PK results only in scrambled format.

## **8.5 Drug Supply**

The investigational site will be supplied initially with a congruous number of suspension bottles, in order to have sufficient supply of study drug to treat the children who are enrolled in the study.

### **8.5.1 Packaging**

The primary packaging will consist of an amber plastic bottle containing the suspension. Givinostat/Placebo oral paediatric suspension is supplied in a 150 mL capacity amber PET bottle closed by means of a red-white HDPE child-proof screw cap with a LDPE shutter/syringe-adapter. Each bottle contains 140 mL of givinostat 10 mg/mL or placebo. The secondary packaging will be a carton box containing one amber bottle and a two syringe for oral use as dosing systems for dispensing the suspension.

### **8.5.2 Labelling**

The primary and secondary labels will show all the information requested according to the Annex 13 of the Good Manufacturing Practice and comply with the legal Investigation use requirements of each country.

Medication labels will be in the local language.

The labels for European countries will include at least:

- Name of the medicinal product
- Pharmaceutical dosage form
- Route of administration
- Quantity of dosage units
- Strength/potency
- Batch number/Packaging number

- Sponsor's study code (\*)
- EudraCT number (\*)
- Investigator name (\*)
- Site and subject number (\*)
- Treatment/Randomization number (\*)
- Name, address, and telephone number of the main contact (the sponsor or the contract research organization or the investigator) (\*) (\*\*)
- Period of use (\*)
- Storage conditions (\*)
- Directions for use (\*) (\*\*)
- For clinical trial use only (\*)
- Keep out of reach of children (\*)

Notes:

(\*) According to Annex 13 and EU law in force, when using a centralized electronic randomization system, some of the listed information may be omitted from the label.

(\*\*) According to Annex 13, such information might not need to appear on the label if separately provided in a leaflet or card.

The labels for United State and Canadian sites will include at least:

- Sponsor's study code
- IND number
- Packaging number
- Name of the medicinal product
- Pharmaceutical dosage form
- Route of administration
- Quantity of dosage units
- Strength/potency
- Batch number
- Expiry date
- Administer as per Protocol
- Caution: Investigational Drug – Limited by Federal (United States) Law to Investigational Use
- Storage conditions
- Keep out of the reach of children
- Sponsor.

### **8.5.3 Storage**

The investigational site will store the study drug under the conditions specified here below, ensuring that it is not accessible to unauthorized persons until it is dispensed to the subject's parent/legal guardian.

Givinostat/Placebo suspension has to be stored in a refrigerated condition at  $5^{\circ}\text{C}\pm 3^{\circ}\text{C}$ . Once the container is firstly opened, the suspension can be administered for a maximum of 30 days.

## **8.6 Treatment Accountability and Compliance**

The study drug packaging will be provided with tear off labels; before treatment dispensation the tear-off label should be removed from the subject's pack by the Investigator and stuck on the appropriate drug accountability form.

At each dispensing visit, the subject's parent/legal guardian will bring back to the study site all bottles previously received (used, partially used and unused) and receive a new supply of the study drug.

Subject compliance will be evaluated through a subject diary indicating how many doses were effectively administered by the subject. .

Compliance will be checked by Italfarmaco S.p.A. or its designee based on the drug accountability documented by the site staff and monitored by Italfarmaco S.p.A. or its designee.

The used, partially used, and unused bottles will be collected and sent back to Italfarmaco S.p.A. or their designee periodically or at the end of the study.

Accountability and compliance is detailed in the relevant CSOM.

## **8.7 Prior and Concomitant Illnesses and Medications**

### ***8.7.1 Prior and Concomitant Illnesses***

Investigators should document all prior significant illnesses that the subject has experienced within 6 months of screening. The starting date of corticosteroids use will be also collected. Additional illnesses present at the time when informed consent is given and up to the time of first dosing (Visit 3) are to be regarded as concomitant illnesses.

Illnesses first occurring or detected during the study and/or worsening of a concomitant illness during the study are to be documented as AEs on the eCRF.

### **8.7.2 Prior and Concomitant Medications**

All medications and other treatments taken by the subject during the study, including those treatments initiated within 6 months prior to the start of the study, must be recorded on the eCRF.

Subjects should be on systemic corticosteroid therapy for at least 6 months prior to initiation of study drug. That is, there have been no changes in systemic corticosteroid therapy (e.g., change in type of drug, dose modification not related to body weight change, schedule modification, interruption, discontinuation, or re-initiation) during the previous 6 months.

As the subjects to be randomised are on stable steroids, the recommended national immunisation schedule, including varicella immunity, should be completed (i.e., as recommended in the “Diagnosis and Management of Duchenne Muscular Dystrophy” guideline), before the Screening Visit.

Concomitant treatments are defined as treatments taken after study drug administration.

Any medication or therapy that is taken by or administered to the subject during the course of the study must be recorded in the eCRF. The entry must include the dose, regimen, route, indication, and dates of use.

After the Screening visit, medication to treat minor treatment-emergent illnesses are generally permitted; supportive treatments, such as anti-emetics, anti-diarrhoeals, anti-pyretics, anti-allergics, analgesics, and antibiotics are allowed.

Use of Vitamin D, calcium and any other supplements if clinically indicated before enrollment and for duration of the study are allowed.

The following therapies are expressly **prohibited** throughout the study:

- Any other investigational drug while on this study,
- any dystrophin restoration product
- use of any pharmacologic treatment, other than corticosteroids, that might have an effect on muscle strength or function (e.g., growth hormone)

The following are concomitant therapy **requiring caution** throughout the study:

- Drugs known to increase the QT interval (see Appendix 16.1 for a list of such compounds).
- Drugs known to be P-glycoprotein inhibitors (see Appendix 16.3 for a list of such compounds).
- Live or live attenuated vaccines: the subject must be carefully monitored. While the decision of the Investigator cannot be influenced, deleted nor approved by the Medical Monitor, it is advised but not mandatory that the Investigator discuss the case with the Medical Monitor before using these vaccines.
- Drugs known to be a substrate of Organic Cation Transporter 2 transporter (see Appendix 16.2 for a list of such compounds).
- Antiplatelets, thrombolytic and anticoagulants drugs: subject must be carefully monitored (i.e. increase the frequency of hematology testing, evaluate any possible sign of bleeding).

## **9 STUDY PROCEDURES**

Table 6 outlines the timing of procedures and assessments to be performed throughout the study. See Section 9.1 for additional details of study procedures.

**Table 6: Schedule of Assessments**

Month	-1		0	1				2		3	6	9	12	15	18	19
Week	-4 	From 1 day after V1 to -2	0	1	2	3	4	6	8	12	24	36	48	60	72	76
Visit window	± 2 weeks	+ 3 days	0	± 3 days	± 3 days	± 3 days	± 3 days	± 3 days	± 3 days	± 7 days	± 7 days	± 7 days	± 7 days	± 7 days	± 7 days	± 7 days from last dose
Visit	V1	V2 	V3	V4	V5 	V6 	V7	V8 	V9	V10	V11	V12	V13	V14	V15	V16
	Screening		Rand												EOS/Early Withdrawal 	FUV 
Informed consent	X															
Eligibility criteria	X		X													
Medical history and demographic data	X															
Prior and concomitant medications	X		X	X			X		X	X	X	X	X	X	X	X
Physical examination	X 		X	X			X		X	X	X	X	X	X	X	X
Vital Signs	X		X	X			X		X	X	X	X	X	X	X	X
Weight	X		X	X			X		X	X	X	X	X	X	X	X
Height	X										X		X		X	
ECG Test 	X		X	X			X		X	X	X	X	X	X	X	X
ECHO	X															X
Pulmonary function tests 	X 												X 		X 	
Serology 	X															
Hematology 	X		X	X	X	X	X	X	X	X	X	X	X	X	X	X
Blood chemistry 	X						X		X	X	X	X	X	X	X	X
Coagulation tests (PT and aPTT)	X								X	X	X	X	X	X	X	X
Urine analysis 	X								X	X	X	X	X	X	X	X
LTBP4 and osteopontin genotype			X													
Exploratory serum Biomarkers			X										X		X	
Quality of life test (assessed by PODCI)	X												X		X	
4 -stairs Climb 	X	X	X							X	X	X	X	X	X	
NSAA + 6MWT	X		X							X	X	X	X	X	X	

Month	-1		0	1				2		3	6	9	12	15	18	19
Week	-4 	From 1 day after V1 to -2	0	1	2	3	4	6	8	12	24	36	48	60	72	76
Visit window	± 2 weeks	+ 3 days	0	± 3 days	± 3 days	± 3 days	± 3 days	± 3 days	± 3 days	± 7 days	± 7 days	± 7 days	± 7 days	± 7 days	± 7 days	± 7 days from last dose
Visit	V1	V2 	V3	V4	V5 	V6 	V7	V8 	V9	V10	V11	V12	V13	V14	V15	V16
	Screening		Rand												EOS/Early Withdrawal 	FUV 
Muscle strength 	X		X							X	X	X	X	X	X	
Cognitive function evaluation	X														X	
PK blood sample collection 							X			X	X		X		X	
Study drug dispensation and accountability			X				X		X	X	X	X	X	X		
Subject diary dispensation and evaluation of drug compliance through diary			X				X		X	X	X	X	X	X	X	
Acceptability/ Palatability evaluation							X								X	
AE assessment	X		X	X			X		X	X	X	X	X	X	X	X
MRI/MRS 		X											X		X	
Genetic Test 	X															

6MWT=6-minute walking test; AE=adverse event; NSAA= North Star Ambulatory Assessment; PODCI= Paediatric Outcomes Data Collection Instrument; PFTs= pulmonary function tests; PT=Prothrombin time; aPPT= activated partial thromboplastin time; ECG= electrocardiogram; ECHO= echocardiogram; PK= pharmacokinetics; MRI= magnetic resonance imaging; MRS= magnetic resonance spectroscopy; FEV1= forced expiratory volume at 1 second; FVC=forced vital capacity; PEF= peak expiratory flow; RBC=red blood cell; WBC=white blood cell; ALT=alanine aminotransferase; AST=aspartate aminotransferase; LDH= lactate dehydrogenase; CRP=C-reactive protein; GGT=gamma-glutamyl transpeptidase; BUN=blood urea nitrogen; fT3= free T3 (the active part of triiodothyronine); fT4=Free T4 (the active part of thyroxine); TSH=thyroid-stimulating hormone; eGFR=estimate Glomerular Filtration Rate; HHM=hand-held myometry; MMT>manual muscle testing

- During screening visit V2, the second Time to 4-stair climb test (4SC) will be performed. The second 4SC can be performed one day after V1 up to a maximum of 2 weeks (+3 days).  
The cognitive function evaluation by Raven coloured progressive matrices could be performed during this visit if not done during the previous one (i.e. V1). Test should be performed at the same time at the beginning and at the end of the study  
MRI/MRS could be performed in a different day (i.e. not necessarily during the same day of Time to 4-stair climb test, due to the fact that the MRI site can be performed in a different site).

2. These visits may be performed by Investigator's authorized personnel outside the site location (e.g., at the subject's home or at the subject's General Practitioner's practice. See conditions in Section 9.1.4)
3. If the subject is discontinued from the study treatment, the subject will be asked to return for the early withdrawal visit to be performed within 2 weeks of the last dose of study drug. In this case, the cognitive function evaluation and MRI/MRS may not be performed.
4. The subjects who complete the study (i.e. 18 months of treatment) will be asked to return to the centre for the Follow up visit to be performed after 4 weeks from the last dose of study drug (i.e. 4 weeks  $\pm$  7 days).
5. During the screening visit V1 and at the end of study (i.e. V15) assessment for ankle range of motion (ROM) should be performed.
6. 12-lead ECG has to be done in triplicate at the screening visit and during the other visits if an ECG demonstrates a prolonged QTcF interval  $>$  450 msec, obtain 2 more ECGs over a brief period, and then use the averaged QTcF values of the 3 ECGs to determine whether the subjects should be discontinued from the study (see Section 7.3.1). 12-lead ECG should be performed at 2,5 hours (i.e 150 minutes)  $\pm$ 30 minutes after drug intake.
7. Pulmonary function tests FEV1, FVC, FEV1/FVC and PEF. In case the test does not achieve ATS criteria and the evaluator does not feel a valid attempt has been made, the subject should repeat the test at randomization if the test is failed at screening visit. If the test is failed at 12 months and/or at 18 months the subject has to be asked to come back to perform the test.
8. Serology: immunoassay methodology for CMV IgM; in-house methodology of chemiluminescence for HBsAg/HCV/HIV; and ECLIA for EBV IgG.
9. Hematology test: CBC:RBC, WBC (including differential count), hemoglobin, MCH, MCHC, MCV, hematocrit, and platelets. Test will be done according to the schedule (i.e., weekly for the first month of treatment, every 2 weeks for the second month of treatment) and are to be performed more frequently if clinically indicated. Note: Repeat visits for the platelets count will be assumed at the request of the Investigator. If the dose is reduced due to platelet count  $\leq$ 150 x 10^9/L, and/or white blood cell  $<$ 3.0 x 10^9/L and/or hemoglobin  $<$ 10.0 mg/dL, a complete blood count (i.e.CBC) test must be performed weekly for 8 consecutive weeks.
10. The following blood tests will be assessed: total bilirubin, direct bilirubin, alkaline phosphatase, amylase, ALT, AST, LDH, cystatin C, CRP, GGT, creatine kinase, total protein, albumin, uric acid, triglycerides, phosphorus, total cholesterol, LDL, HDL, sodium, potassium, chloride, calcium, glucose, creatinine, BUN, TSH, fT3, fT4, bicarbonate). Note that TSH, fT3, and fT4 will be taken at Visits 7, 9, 10, 11, 12, 13, 14, 15 and 16.
11. Urinalysis: appearance, pH, specific gravity, protein, glucose, ketone bodies, blood and WBCs, and urobilinogen.
12. During the screening period (i.e., 4 weeks  $\pm$ 2), time to 4-stair climb test (4SC) should be performed at V1 and V2. The 4SC at V2 can be performed one day after V1 up to a maximum of 2 weeks (+3 days). For this reason the subjects should go to the centre 2 times (i.e., Visit 1 and Visit 2). The test should be video recorded during Visit 1, Visit 3, Visit 13 and Visit 15.
13. Muscle strength tests: at screening: knee extension, elbow flexion by HHM and knee extension by MMT. During the study and at the end: knee extension, elbow flexion by HHM.
14. Pharmacokinetic sample collection: sampling (2 pre-dose during the treatment and 4 post-dose) will be collected as described in the protocol during the following visits: 7 (4 weeks), 10 (12 weeks), 11 (24 weeks), 13 (Week 48) and 15 (Week 72). At these visits, the subject will be asked to take the morning dose at site.
15. The baseline MRI/MRS test has to be performed when all inclusion/exclusion criteria have been already evaluated and the subject is eligible. At screening all subjects will perform the MRI of thigh and MRS of vastus lateralis; then the MRI of thigh and MRS of vastus lateralis will be performed also at 12 and 18 months in a subgroup of subjects: the first 99 - 150 randomised subjects in the target population (i.e. with MRS VL MFF between  $>$  5% and  $\leq$ 30%). The MRI evaluation using Dixon technique and the MRS will be performed at specialized sites.
16. Genetic test should be performed only in case it is not already available.

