## 9.1 Procedures by Study Visit

There will be at least 15 study visits, including the Screening and Randomisation Visits.

Assessments will be performed as outlined in the following by-visit subsections. As platelets count reductions are observed after treatment with givinostat, study site personnel who will perform functional tests and MRI/MRS must be different from the personnel who will review subjects' safety results and safety results must not be shared with the personnel responsible for the functional tests and MRI/MRS.

At the discretion of the Investigator, subjects not meeting inclusion/exclusion criteria may be re-screened twice with an interval of at least 3 months between assessments.

If needed, safety assessments (e.g. blood test, unscheduled visits) may be performed at the subject's home by a local qualified nurse trained in the study protocol.

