**9.1.8 Visit 15: End of Study Visit (also named “EOS Visit”, Week 72 ± 7 days), and early withdrawal visit**

At the end of the treatment (i.e., 72 weeks after the Randomization Visit, ± 7 days) the EOS Visit (Visit 15) will be scheduled. At EOS Visit the subject should take the morning dose at the site.

Subjects who prematurely withdraw from the study for any reason will perform an Early Withdrawal Visit within two weeks after the last study drug dose intake. The Early Withdrawal Visit requirements are the same as the EOS Visit (Visit 15) described in this section.

If the Early Withdrawal Visit or the EOS Visit is not done, the reason will be recorded in the CRF.

At this Visit 15, the following assessments will be performed unless otherwise noted:

- Collect and record concomitant medications;
- Perform a physical examination (at V15 assessment for ankle ROM should be done)
- Measure vital signs (blood pressure, pulse rate, and body temperature);
- Measure weight;
- Measure height;
- Perform a 12-lead ECG (at 2,5 hours ±30 minutes after drug intake);
- Perform an ECHO;
- Perform pulmonary function tests: FEV1, FVC, FEV1/FVC, and PEF;
- Collect blood samples for:
  - hematology;
  - blood chemistry;
  - coagulation tests (PT and aPTT);
- Collect DMD serum biomarkers;
- Obtain a urine sample for urine analysis;

- Obtain PK blood sample. The remaining PK samples may be drawn during this visit in order to obtain all required PK samples;
- Perform Quality of Life test (assessed by PODCI);
- Perform time to 4SC
- Perform NSAA and 6MWT;
- Perform muscle strength tests
- Perform cognitive function evaluation (test should be performed at the beginning and at the end of the study, at the same time of the day);
- Perform acceptability/palatability evaluation;
- Evaluation of drug compliance through diary;
- Assess AEs;
- Perform MRI/MRS evaluation (MR cohort only). (If the subject is discontinued from the study treatment, the subject will be asked to return for the early withdrawal visit to be performed within 2 weeks of the last dose of study drug. In this case, the cognitive function evaluation and MRI/MRS may not be performed).

Functional tests will be video recorded.

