The subject has to be asked to attend an unscheduled visit to repeat measurement of pulmonary function as assessed by spirometry if the test performed at visit 15 has not met ATS/ERS criteria and/or the evaluator has deemed that a valid attempt to perform a correct maneuver was not made by the subject.

At visit 15, the subject's parent/legal guardian will be asked to consent in writing and subject to assent and/or consent in writing for his participation in the long-term study. In case the subject or parent/legal guardian do not provide assent/consent, a final Follow-up visit will be performed.

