#### **12.4 Echocardiogram**

Standard ECHOs will be conducted at the visits indicated in the Schedule of Assessments, Table 6, and more often if clinically indicated.

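### Protocol Table 6 marks the only post-baseline ECHO at the follow-up visit (V16), not at V15 as Section 9.1.8 requires, and its footnote 4 omits the condition for holding V16

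*Protocol*

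**What the plan says.** The protocol gives two sources for what is done at each visit. Section 9 says "Table 6 outlines the timing of procedures and assessments to be performed throughout the study". Section 9.1 says "Assessments will be performed as outlined in the following by-visit subsections". For the echocardiogram, Section 12.4 chooses the table: "Standard ECHOs will be conducted at the visits indicated in the Schedule of Assessments, Table 6, and more often if clinically indicated".

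The places that fix the post-baseline ECHO are:

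- **Table 6, ECHO row:** marked at V1 (screening) and V16 (follow-up visit, Week 76). The V15 cell (EOS/Early Withdrawal, Week 72) is empty.
- **Section 9.1.8 (V15):** the list includes "Perform an ECHO", and for boys who stop early, "The Early Withdrawal Visit requirements are the same as the EOS Visit (Visit 15) described in this section".
- **Section 9.1.9 (V16):** no ECHO in the list.

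The places that say who attends V16 are:

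- **Table 6, footnote 4:** "The subjects who complete the study (i.e. 18 months of treatment) will be asked to return to the centre for the Follow up visit", with no condition.
- **Section 9.1.8:** "In case the subject or parent/legal guardian do not provide assent/consent, a final Follow-up visit will be performed", where the consent in question is to the long-term study. Sections 6.1 and 9.1.9 and SAP 2.3 set the same restriction.

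Change in cardiac function by ECG and ECHO from baseline to end of study is a listed safety endpoint (Section 5.2.3). SAP 5.6 summarises ECHO values and change from baseline by visit. SAP 2.8 maps Week 72 data to EOS or Early Withdrawal and presents Week 76 data as their own visit.

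**The concern.** The table that Section 12.4 names for ECHO timing disagrees with the visit text about the only scheduled post-baseline ECHO. A coordinator working from Table 6 would not order an ECHO at Week 72. Two things could follow. The ECHO could be taken at Week 76, after the boy has stopped study drug, and be reported under that visit and not as the end-of-study value. Or it could be missed in a boy who goes into the long-term study and therefore has no V16.

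Footnote 4 is a second, separate defect. It calls all completers back for a visit that four other places restrict to boys who do not enter the long-term study.

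**Working it through.** No power, alpha or sample-size figure is involved. The check compares the table with the visit lists.

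**1. Position of the ECHO mark.** The visit header of Table 6 has 17 fields: the row label plus V1 to V16. The ECHO row also has 17 fields, with marks in the V1 and V16 positions. Other sparse rows fall where the visit text puts them: height at V1, V11, V13 and V15; pulmonary function at V1, V13 and V15; cognitive function at V1 and V15. A general column shift therefore does not explain the V16 mark.

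**2. Table 6 against Section 9.1.8 (V15).** With the blood tests counted separately and NSAA and 6MWT as one, Section 9.1.8 lists 23 procedures: concomitant medication, physical examination, vital signs, weight, height, ECG, ECHO, pulmonary function, hematology, chemistry, coagulation, serum biomarkers, urine, PK, PODCI, 4SC, NSAA with 6MWT, muscle strength, cognitive function, palatability, diary compliance, AEs and MRI/MRS. Table 6 marks 22 of them at V15. The difference, 23 − 22 = 1, is the ECHO.

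**3. Table 6 against Section 9.1.9 (V16).** Table 6 marks 11 procedures at V16. Section 9.1.9 lists 9: concomitant medication, physical examination, vital signs, ECG, hematology, chemistry, coagulation, urine and AEs. The difference, 11 − 9 = 2, is ECHO and Weight. Weight is also marked at V15, so its end-of-study value is not at risk. ECHO is the only one of the 11 with V15 blank.

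**4. Timing of an ECHO taken at V16.** The follow-up visit is 4 weeks ± 7 days after the last dose: 28 − 7 = 21 days to 28 + 7 = 35 days. The V15 ECHO would be taken at Week 72, on treatment.

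**5. Who could be affected, by how the site reads the protocol.**

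| Site follows | Boy | ECHO |
|---|---|---|
| Section 9.1.8 | any | at V15 or Early Withdrawal, as intended |
| Table 6 with footnote 4 taken literally | any completer | at V16, late but not missed |
| Table 6 mark, with the V16 condition from Section 6.1, 9.1.8 or 9.1.9 | completer who declines the long-term study | at V16, late |
| Table 6 mark, with the V16 condition from Section 6.1, 9.1.8 or 9.1.9 | completer who enters the long-term study | none scheduled |

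For early stoppers, Section 7.3 defines the final evaluation by Section 9.1.8, and Section 7.3.1 sends boys stopped for safety to the EOS visit in that section. Footnote 3 allows only cognitive function and MRI/MRS to be left out at early withdrawal.

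**6. Footnote 4.** This is running text, so it does not depend on how the table cells were read. It conflicts with Sections 6.1, 9.1.8 and 9.1.9 and with SAP 2.3.

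**The case against.** The strongest reply is that the operative text is already right. Section 9.1 makes the by-visit subsections govern, Section 9.1.8 has the ECHO at V15, and a site following it makes no error. That stands, and it is why V15 is the evident intent. It does not remove the conflict, because Section 12.4 sends the reader to the table.

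A second reply is that the ECHO point rests on one cell in a table read from a PDF. Equal field counts rule out a shifted row but not a single misplaced mark. This also stands: the cell must be confirmed in the PDF. The footnote point is unaffected.

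Third, a reader might infer that boys who stop early lose their ECHO, that every boy who rolls over loses it, or that an ECHO taken at V16 drops out of the analysis. The documents do not support any of these:

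- Sections 7.3, 7.3.1 and 9.1.8 together direct early stoppers to a list that contains the ECHO.
- Loss in a boy who rolls over requires a site to take the mark from Table 6 and the visit condition from elsewhere. Read literally together, the table and footnote 4 give a late ECHO, not a missing one.
- SAP 2.8 still presents Week 76 data, and SAP 5.6 summarises ECHO by visit. A V16 ECHO would be reported, but not as the EOS value.

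Finally, absence from Section 9.1.9 is not peculiar to ECHO, since Weight shows the same mismatch at V16. The distinctive evidence is the blank V15 cell.

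**Conclusion.** The inconsistency holds, subject to confirming the ECHO cell in the PDF. Table 6 puts the only scheduled post-baseline ECHO at V16, against Sections 9.1.8 and 9.1.9. Footnote 4 is incomplete whatever the cell shows.

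The size is minor. A site scheduling from Table 6 could take the ECHO 21 to 35 days after the last dose, or miss it in a boy who enters the long-term study. The documents do not allow the number of such boys to be estimated. One descriptive safety endpoint is touched. The primary endpoint, alpha and sample size are not.

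**What to change.** After checking the PDF:

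- In the ECHO row of Table 6, move the second mark from V16 to V15 (EOS/Early Withdrawal).
- Add to footnote 4 that V16 is held only if the subject or parent/legal guardian does not consent to the long-term study.
- Reconcile Weight at V16, either by removing the mark from Table 6 or by adding weight to Section 9.1.9.

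The ECHO and footnote changes cost one table mark and one clause, with no added visit or procedure. The Weight correction is a one-item edit to a visit that already takes place.
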